The APRIL Trial initially planned to recruit up to 2500 patients via a remote recruitment model, however this protocol was not approved by the regulator (MHRA) so it was agreed that the trial would recruit through NHS GP surgeries until sufficient safety data was gathered (at least 100 patients) to support modifying the monitoring protocol to allow faster recruitment. However, it took longer than anticipated to recruit the first 105 patients by which time the Long COVID patient numbers, NHS support for Long COVID services and other factors had changed considerably. It was therefore decided by the Trial Steering Committee that the trial should be halted with the initial 105 patients recruited, and trial data analysed, to inform decisions around the design of a future trial and inclusion of the most appropriate individuals. The original set of analyses will still be conducted as laid out in the protocol although the primary outcome analysis is expected to be underpowered (based on the effect size assumptions in the original power calculation). The safety outcome analyses are anticipated to be particularly informative, given the absence of quality clinical data on the safety profile of Ashwagandha for this patient population. This may help to inform the general public regarding the safety of their usage of Ashwagandha (which is a popular over-the-counter supplement) as well as the design of future randomised trials of this product.

2 Study Objectives

Primary – to determine the effectiveness of Ashwagandha tablets (3-month course) for improving functional status at 3 months (measured by the Post-COVID-19 Functional Status Scale) among people experiencing ongoing symptoms of COVID-19.

Secondary – to determine the safety of Ashwagandha tablets (3-month course) and effectiveness for improving quality of life, reported fatigue, breathlessness, pain, sleep quality, mental health, cognitive function, work status and other symptoms at 3 months.

3 Study Design

3.1 Overall design

This is a randomised double-blind placebo-controlled trial. Interested individuals who have a diagnosis of Long COVID (and conform to all other eligibility criteria) were randomised to take Ashwagandha or placebo for 3 months (delivered at home by post). Participants were recruited through participating GP practices or NHS Long Covid Clinics (hereafter referred to as clinical trial sites). Follow-up for functional status, quality of life and other self-reported outcomes was by online or postal surveys (as per participant preference) conducted monthly. Follow-up for

safety was through clinical assessment by the study investigator's clinical team, conducted monthly.

3.2 Sample size

The original sample size planned for the trial was 2500. The justification for this given in the study protocol is as follows: "Published data from an online survey of Long COVID patients indicate that patients' grade distribution on the Post-Covid Functional Scale (scale 4 (severe) to 0 (none)) improved from of 3.4, 49.4, 35.1, 7.1 and 5.0% at 3 months to 2.1, 43.9, 35.1, 10.5 and 8.4% at 6 months². If Ashwagandha can improve symptoms to a similar extent at 3 months, this translates to an overall odds ratio of 0.71 on the ordinal logistic regression analysis (with an odds ratio less than one indicating a shift to a lower grade of symptoms). In order to improve symptoms with a more modest odds ratio of 0.75, a sample size of 2500 gives in excess of 90% (or 80% power to detect an even more conservative odds ratio of 0.80). An odds ratio of 0.75 would result in the percentages in each grade (grades 4 to 0) being 2.6, 43.1, 38.8, 9.0 and 6.6% in the Ashwagandha arm at end-line. The primary analysis will include adjustment for the baseline value of the primary outcome scale which is expected to increase the power further."

This sample size was proposed initially alongside a more simplified trial protocol in which Long COVID patients registered their interest online, were randomised online, and then posted the medications directly from the trial coordinating centre. However this model (which would have allowed much more rapid recruitment) was not permitted by the regulator (MHRA) who required clinician oversight of each patient including regular liver function monitoring. The MHRA-directed approach was adopted, which involved modifying the protocol to recruit and monitor through NHS GPs. It was agreed with the MHRA that after safety and effectiveness data from at least ~100 patients' had been gathered, we would submit the safety information and apply to relax the monitoring procedures to speed up recruitment. This initial safety-focussed phase of the trial has been completed although we opted not to continue the trial because of barriers faced in identifying and recruiting Long COVID patients. The trial is therefore expected to be underpowered for the primary outcome, although they will still be presented in adherence with the pre-specified protocol, and emphasis will be placed on the safety-related trial outcomes.

3.3 Randomisation

In this trial we conducted blinded web-based randomisation in 1:1 ratio after initial consent. Block randomisation (randomly permutated blocks) with varying block size were used to ensure balance throughout the recruitment period.

3.4 Study Assessments

3.4.1. Trial outcomes

Primary outcome measure

Self-reported functional status measured using the Post-COVID-19 Functional Status Scale (PCFS), at 3 months². Functional status is a key patient-centred indicator which measures the extent to which a condition limits a person's ability to conduct their usual activities. The PCFS has gained widespread popularity as a tool for measuring self-assessed functional status in Long COVID in trials and observational studies and has been translated into multiple languages. It was based on a similar, widely-used functional scale for stroke patients, and has been

validated in Long COVID patients³. The PCFS asks patients to consider a flow-chart of options that describe the extent of limitations to their daily activities over the past week. Based on the flow chart, they assign themselves to a grade between 0 (no functional limitations) to 4 (severe functional limitations).

Secondary outcome measures (all at 3 months)

- Quality of life by PROMIS 29+2 summary score,
- Self-reported fatigue, pain, sleep, anxiety, depression and social, physical and cognitive function by PROMIS 29+2 individual dimensions
- Self-reported breathlessness by modified MRC Dyspnoea Scale
- Health utility by EQ 5D-5L utility score
- Work status and productivity
- Other self-reported symptoms

Outcomes domains were selected to cover the most relevant key indicators for patients and policy makers as well as the most common symptoms of Long COVID. Outcome questionnaire instruments were chosen following thorough review of the literature and other ongoing studies, on the basis of wide use/validation, short length (to reduce participant burden), and relevance for this study population (ideally used successfully in Long COVID patients before). For outcome scores that required derivation, the approach used in the primary publication will be applied (PROMIS scores⁴ and EQ 5D-5L utility score⁵ using the most recent UK-based value set).

Safety outcomes

- SUSARs
- Severe adverse events (including pregnancies)
- All adverse events
- Adverse events related to liver function abnormalities
- Liver function test parameters

3.4.2 Follow-up for trial outcomes

Follow-up was conducted through a brief monthly online or postal survey of self-reported functional status, alongside secondary outcome measures such as quality of life, fatigue, breathlessness, pain, mental health, sleep quality, work status, and other symptoms, and brief questions on intervention adherence.

Participants were followed-up for 3 months (i.e., end of month 1, end of month 2, end of month 3). Automated email or text reminders were sent as per participant preference. In case participants were unable or unwilling to complete surveys online, paper questionnaires in prepaid return envelopes were posted each month along with the supplement/placebo packages.

For the purposes of analysis, the target outcomes of interest are at 3 months, and this will be operationalised as the outcome data available nearest to completion of 90 days of trial medication, within a maximum of 30 days either side of this date. This means, for example, if both the second month and third month survey were delayed by 3 weeks, the second month survey will be used as this will be closer to the target outcome date of day 90.

3.4.3 Clinical monitoring

The investigator's clinical team assessed all participants at least monthly and conducted symptom-guided assessment as described in NICE Long Covid guidelines. Assessments took place at end of 30 days (±3 days, 1st interim assessment), 60 days (±3 days, 2nd interim assessment) and 91 days (final end of trial assessment) since treatment initiation. At each assessment, they actively elicited the participant's history related to a) any worsening of their Long covid, b) exacerbation of any other pre-existing conditions, and c) any side effects that might be related to the drug (including AE/SAE assessment if applicable). To guide assessment of c), we provided the clinical teams with full list of possible of side effects that have been observed for the trial product (regardless of whether causally attributed). Monthly assessments were conducted remotely or in-person, as per preference of the investigator or participant. Following the initial assessment, further in-person follow-up including any indicated tests and investigations were sought if needed based on participant's symptom assessment, and as guided by relevant local and national guidelines. In particular we highlighted the following areas of assessment: cardiac chest pain, symptoms suggestive of liver or kidney problems, and worsening of psychiatric symptoms.

In addition to these monthly clinical assessments, liver function tests (AST, ALT and bilirubin) were conducted at 30 days (i.e., along with first interim clinical monitoring assessment) and 91 days (i.e., at the end of trial assessment). The test at 30 days was intended to check for any early acute liver toxicity associated with the trial medication, while the test at 91 days was intended to assess for any longer-term effects associated with cumulative build-up of the product in the system. Additional liver function tests could be ordered by the study investigator at any point as deemed clinically indicated for the patient. All WOCBP had to complete an urine pregnancy test monthly during the trial. These tests were done after completing 1st and 2nd month of trial treatment, and after completing 3rd month's treatment at the final end of study assessment, to confirm that no pregnancies occurred during the trial treatment phase.

4 Statistical Analysis approach

4.1 General

Statistical analysis will be performed as pre-specified in this SAP. Any, post-hoc, exploratory analyses completed to support planned analyses, which were not identified in this SAP, will be documented and reported in the relevant trial reports. Any results from unplanned analyses will be clearly identified in the text of the trial reports.

4.2 Time points for analysis

All final, planned, analyses identified in the protocol and in this SAP will be performed only after the last patient has completed their 90-day follow-up. In addition, no database may be locked, randomisation code unblinded, or analyses completed until this SAP has been approved.

4.2.3 Interim analyses

There were no planned or conducted interim analyses for this trial. The Independent Data Monitoring Committee examined safety data stratified by trial arm (not unblinded) on a 3-monthly basis as part of their safety monitoring. No member or attendee of the closed part of the Data Monitoring Committee has any input into the content or writing of this SAP.

4.3 Pooling of sites

Data from each participating trial site (GP or Long COVID Clinic) will be pooled for all analyses.

4.4 Definition of study populations for analysis

4.4.1 Intention-to-treat

The primary analyses will be on an intention-to-treat basis, that is, participants will be considered to belong to the trial arm that they were assigned to (even if they did not end up completing the treatment).

4.4.2 Per protocol

Additional analyses on a per-protocol basis will also be conducted, in which participants will be stratified into groups in terms of whether they took the trial treatment or not. The following groups will be analysed:

- Adherers: People who took at least 50% of the intended dose of treatment for at least 60 days (2 months) out of the total 90 days of treatment.
- Non-adherers: All others.

4.5 Methods for handling withdrawals and missing data

There were two types of withdrawal in the trial – complete withdrawal and partial withdrawal.

- Complete withdrawal was when patients discontinued trial medication AND discontinued completing the monthly outcome questionnaires.
- Partial withdrawal was when patients discontinued trial medication but participants continued to complete the monthly outcome questionnaires.

Patients who withdrew from trial medication but continued to participate in follow-up will be analysed according to the intention-to-treat and per protocol definitions described above (4.4).

Complete withdrawals (people who did not complete an endline survey or clinical monitoring), or people who have endline data missing for any other reason, will be excluded from the primary analysis of outcomes at 3 months. Outcome data will not be imputed in the primary analysis models. Additional analyses will be undertaken using data from the 1st, 2nd and 3rd months' follow-up only to explore how timing of outcome assessment influenced the results (described in section 8.2 below).

4.6 Statistical analysis software

Statistical analysis will be conducted using R or Python Software and the version will be stated in the study report. Statistical analysis code will be published along with the study report.

5 Descriptive analyses

Continuous variables will be described by the means and standard deviation except for skewed variables which may be described by the median and inter quartile range (IQR). Categorical

variables will be described by frequency and percentages in each category by treatment group (see appendix table 1).

Description of the follow-up of participants by trial arm (i.e. number completing months 1, 2 and 3 medication and surveys) will be presented graphically in a flow chart.

Description of adherence to medication and timeliness of survey completion and clinical monitoring by trial month (for participants not completely withdrawn or lost) will be tabulated (see appendix table 2).

6 Evaluation of patient-reported outcomes

6.1 Primary outcome

The primary analysis of the primary outcome will be an intention-to-treat complete case analysis at 3-month follow-up, adjusted for baseline level of the same outcome. Post-Covid Functional Status Scale will be analysed using ordinal logistic regression. No other adjustments will be made for the primary analyses, although additional secondary analyses adjusting for age (above or below median) and gender will be conducted (see section 8.4 below).

6.2 Secondary outcomes

Due to the large number of secondary outcomes, the PROMIS-29+2 summary score and EQ-VAS score will be considered as 'key secondary outcomes' and only these (along with the primary outcome) will be taken forward into the additional analyses (section 8). For all secondary outcomes, the main analysis will be intention-to-treat complete case analysis at 3-month follow-up, and for continuous and ordinal outcomes these will be adjusted for baseline level of the same outcome. The statistical models that we plan to use for each outcome are listed below. Distributional checks will first be conducted to ensure that key assumptions for each planned model type are met, and if for any given outcome there are violations that threaten the validity of the proposed model type, that outcome will be binarized by the median value and analysed with binary logistic regression.

Ordinary least squares (linear) regression:

- Quality of life by PROMIS 29+2 summary score
- Self-reported fatigue by PROMIS 29+2 fatigue dimension
- Self-reported sleep disturbance by PROMIS 29+2 sleep dimension
- Self-reported anxiety by PROMIS 29+2 anxiety dimension
- Self-reported depression by PROMIS 29+2 depression dimension
- Self-reported social participation by PROMIS 29+2 social function dimension
- Self-reported physical function by PROMIS 29+2 physical function dimension
- Self-reported cognitive function by PROMIS 29+2 cognitive function dimension
- Self-reported pain interference by PROMIS 29+2 pain dimension
- Self-reported pain intensity by PROMIS 29+2 0-10 pain rating scale
- Health utility by EQ 5D-5L utility score
- EQ VAS score
- Self-reported work productivity by 0-10 scale on the work questionnaire (people out of work scored to 0)

Ordinal logistic regression:

- Self-reported breathlessness by modified MRC Dyspnoea Scale
- Other self-reported symptoms number (count) of other symptoms experienced (grouped into 5 groups according to the distribution)

Binary logistic regression

- Whether any hours of work were missed in the past 7 days (yes/no) (people out of work set to no)
- Other self-reported symptoms binary presence/absence of each of the 22 other symptoms asked (only including in the table those with at least 10 individuals reporting that symptom at baseline). If any other self-reported symptom (from the free-text field) was reported by at least 10 people at baseline, this can also be added.

Dummy table illustrating the presentation of the primary and secondary analysis results is given in appendix table 3.

7 Evaluation of safety outcomes

A table will be presented with counts of the following adverse safety outcomes, by trial arm (appendix table 4):

- SUSAR
- Serious adverse event (SAE)
- Pregnancy
- Adverse reactions involving abnormal liver test results (adverse event designated as probably or definitely related to trial medication)
- All other adverse reactions
- Adverse events (designated possible or unlikely related to trial medication) involving abnormal liver test results
- All other adverse events (designated possible or unlikely related to trial medication)

Further description and discussion of any SUSAR, SAE, pregnancy, adverse reactions and abnormal liver test results will be provided in the text (as the numbers of these are anticipated to be few). For each abnormal liver test result, the status of liver function at baseline will be mentioned, as abnormal liver function at baseline is expected to be linked to abnormal results during follow-up (although numbers are expected to be too small to formally test this). All adverse events will be broken down into specific categories (e.g. headache, nausea, etc) by trial arm in an appendix table. We will also present adverse events by trial arm stratified by gender in the same appendix table.

Changes over time in liver function test (LFT) results by arm will be described through data visualisation. Specifically, we will plot the mean and standard error values of AST, ALT and bilirubin at baseline, month 1 and month 3 by trial arm. T-test for the differences in each LFT will be calculated at each timepoint, crudely and with adjustment for baseline level. The corresponding numerical results will be given in an appendix table.

8 Additional analyses

The following additional analyses will only be applied to primary and key secondary to avoid multiplicity of analysis results. Apart from the specific aspects mentioned, each analysis will be the same as described in section 6.

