Appendix Table 3: Dummy table for primary and secondary patient-reported outcome analyses

	Outcome at 3-months		Effect size (95% CI)	P-value
	Intervention	Control arm	for intervention vs	
	arm (N=)	(N=)	control*	
Primary outcome: PCFSS (N and %)	*			•
0 – no limitations				
1 – negligible limitations				
2 – occasional limitations				
3 – some limitations				
4 – severe limitations				
Key secondary outcomes (mean and	SD)			•
Quality of life by PROMIS 29+2				
summary score				
Quality of life by EuroQol Visual				
Analogue Scale (0-100)				
Secondary outcomes (mean and SD	or N and %)			
Fatigue (PROMIS score)				
Sleep disturbance (PROMIS score)				
Anxiety (PROMIS score)				
Depression (PROMIS score)				
Social participation (PROMIS score)				
Physical function (PROMIS score)				
Cognitive function (PROMIS score)				
Pain interference (PROMIS score)				
Pain intensity				
Breathlessness♦				
Health utility (EQ-5D-5L)				
Missed work●				
Work productivity				
Symptom burden◆				
Symptom 1 (TBC) ●				
Symptom 2 (TBC) ●				
Symptom 3 (TBC) ●				

^{*}Adjusted for baseline level of outcome. Effect sizes represent mean difference in outcome score between intervention and control arms unless otherwise specified: ♦ = Odds ratio from ordinal logistic regression, • = Odds ratio from binary logistic regression.

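### Section 6.2 specifies baseline adjustment for continuous and ordinal secondary outcomes only, while the Appendix Table 3 footnote labels the binary odds ratios as adjusted too

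*SAP*

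**What the plan says.** SAP section 6.2 sets an intention-to-treat complete-case analysis at 3 months for every secondary outcome and then adds that "for continuous and ordinal outcomes these will be adjusted for baseline level of the same outcome". It lists three model classes: linear, ordinal logistic and binary logistic. The adjustment sentence covers the first two.

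The binary class holds two kinds of outcome:
- Missed work: "Whether any hours of work were missed in the past 7 days (yes/no) (people out of work set to no".
- Symptoms: "Other self-reported symptoms binary presence/absence of each of the 22 other symptoms asked", plus frequently reported free-text symptoms. The symptoms tabulated are restricted by baseline frequency: "only including in the table those with at least 10 individuals reporting that symptom at baseline".

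Section 6.2 also has a fallback. If a planned model's assumptions fail, "that outcome will be binarized by the median value and analysed with binary logistic regression". It does not say whether such an outcome keeps its baseline covariate.

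Appendix Table 3 has one effect-size column, starred to a footnote: "Adjusted for baseline level of outcome. Effect sizes represent mean difference in outcome score between intervention and control arms unless otherwise specified". The same footnote gives the marker carried by the missed-work and symptom rows: "Odds ratio from binary logistic regression". It exempts no row from the adjustment.

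**The concern.** The two places give different instructions for the same estimates. An analyst working from section 6.2 would fit crude logistic models for the symptoms and missed work. One working from the table would include the baseline value. If the choice is left until the data are unblinded, it could be influenced by the results.

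The SAP gives no reason for treating binary outcomes differently. Baseline symptom presence must be held, because it decides which symptoms are tabulated. Section 3.2 expects baseline adjustment to raise power for the primary outcome, and section 7 plans baseline-adjusted comparisons of the liver tests. Section 8 does not fill the gap: it is confined to the primary and key secondary outcomes, so the covariate-adjusted analyses in 8.4 never reach the symptoms.

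The stakes are precision, sensitivity to chance differences between arms at baseline, and a table label that may not match the model fitted.

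**Working it through.** **The plan's own figure.** The SAP gives no power for the binary outcomes. Its only power figures concern the primary outcome (section 3.2). With Whitehead's formula, power = Φ(√(N(1 − Σp̄³)/12) × |ln OR| − 1.96), two-sided 5% assumed:
- Control grades 4 to 0: 3.4, 49.4, 35.1, 7.1, 5.0%. At OR 0.75 these shift to 2.6, 43.1, 38.9, 9.0, 6.6% (the SAP prints 38.8, a rounding difference).
- Mean proportions 0.030, 0.4625, 0.370, 0.0805, 0.058 give Σp̄³ ≈ 0.150.
- √(2500 × 0.850/12) × 0.288 − 1.96 ≈ 1.87, so power is 96.9%, in line with the stated figure of over 90%.
- OR 0.80 gives 84.2% against the stated 80%. Neither figure bears on this point.

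**Chance baseline imbalance.** Inputs: 105 patients (SAP introduction) and 1:1 permuted blocks with no stratification by symptom mentioned (section 3.3). The SD of the between-arm difference in baseline prevalence p is √(4p(1 − p)/105):
- p = 50%: √(1/105) = 9.8 points
- p = 30%: √(0.84/105) = 8.9 points
- p = 10%: √(0.36/105) = 5.9 points

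**Effect on a crude 3-month comparison with no drug effect.** The shift is the imbalance times the gap in 3-month prevalence between those with and those without the symptom at baseline. Persistence is assumed, because the SAP gives none. At 80% versus 20%, one SD shifts the crude difference by 0.6 × 9.8 ≈ 6 points and two SDs by about 12. At 60% versus 40%, one SD shifts it by 0.2 × 9.8 ≈ 2 points. If all 22 symptoms are analysed, about 22 × 0.32 ≈ 7 are expected to exceed one SD and 22 × 0.046 ≈ 1 to exceed two. Given an imbalance of about 19 points and 80%/15% persistence, simulation under no effect has the crude test rejecting in 21% of trials and the adjusted test in 5%.

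**Power.** Logistic regression of the 3-month outcome on arm, with and without baseline presence; Wald test; 4,000 simulated trials per scenario (simulation SE at most 0.8 points). Trials in which the adjusted model failed count as non-rejections in the first table. Prevalence, persistence and effect size are all assumptions.

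Conditional OR 0.35, 52 per arm:

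| Baseline prevalence | 3-month prevalence if present / absent at baseline | Unadjusted | Adjusted | Gain |
|---|---|---|---|---|
| 50% | 60% / 40% | 70.8% | 70.9% | 0.1 |
| 50% | 70% / 30% | 60.7% | 65.5% | 4.8 |
| 50% | 80% / 20% | 43.1% | 54.8% | 11.7 |
| 50% | 90% / 10% | 17.9% | 29.3% | 11.4 |
| 30% | 70% / 15% | 36.0% | 46.5% | 10.5 |
| 10% | 60% / 5% | 6.0% | 7.2% | 1.2 |

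50% prevalence, 80%/15% persistence, 105 patients, varying the conditional OR:

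| OR | Unadjusted | Adjusted | Gain |
|---|---|---|---|
| 0.30 | 45% | 62–63% | 17–18 |
| 0.50 | 18% | 25% | 7 (up to 9 on repeat runs) |
| 0.71 | 8% | 10% | 2 |
| 0.75 | 7% | 8% | 1 |
| 0.80 | 6% | 6% | 0 |

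With no effect, averaged over randomisations, the first set of scenarios rejects in 3–5% of trials unadjusted and 2–5% adjusted. At 10% prevalence, about the SAP's ten-person floor, the ordinary adjusted model fails through separation in about 14% of trials at OR 0.35.

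**The case against.** The strongest reply is that no passage says the binary outcomes go unadjusted. Section 6.2 is silent on them and the table labels them adjusted, so a fair reading is that 6.2 is merely incomplete. The appendix also says that table format may vary. This stands in part. A reader might infer that crude odds ratios will certainly be published under a false label, but the document establishes only a conflict between two passages.

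A reader might also infer that the symptom results would be invalid. They would not: the crude confidence interval already reflects chance imbalance, and type I error is held. The 21% rejection rate is conditional on an unusually large imbalance.

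Nor is a power rise such as 45% to 62% typical. It needs strong persistence and an odds ratio of 0.30, whereas section 3.2 contemplates 0.71 to 0.80, for the primary outcome only. In that range the gain is 0 to 2 points.

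Two further limits stand. For work, the baseline table (Appendix Table 1) shows only whether people were in work, so baseline missed work is not shown to be collected. Adjustment also has a cost for the sparsest symptoms, where ordinary logistic models can separate.

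The stakes are low as well: these outcomes are not key secondaries, section 3.2 already calls the trial underpowered and puts the emphasis on safety, and overall symptom burden is analysed as an ordinal count that 6.2 does adjust. None of this removes the conflict or supplies a rule for binary outcomes.

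**Conclusion.** The point holds as an inconsistency with a modest cost in precision. Section 6.2 by implication leaves missed work and up to 22 symptoms unadjusted, and the Table 3 footnote says otherwise. The unadjusted analysis is valid but less efficient, and it passes chance baseline differences through to the estimate. The imbalance SD of 9.8 points depends only on 105 patients and an assumed 50% prevalence. The power gain depends on assumed prevalence, persistence and effect size: about 0 to 2 points with weak persistence or odds ratios near 0.75, and about 10 to 18 points with strong persistence and a large effect. Near the ten-person floor there is almost nothing to gain. The change is worth making because it is cheap and settles the conflict, but it does not threaten the trial's main conclusions.

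**What to change.** Before unblinding, extend the adjustment sentence in section 6.2 to binary outcomes:
- Symptoms: adjust for baseline presence or absence of the same symptom.
- Outcomes binarized under the fallback: adjust for the baseline value of the same measure.
- Missed work: adjust for its baseline value if collected, otherwise for baseline work status.
- Sparse data: state in advance that Firth-penalised logistic regression, or a similar method, is used when the ordinary model separates or cannot be estimated.
- Label the binary odds ratios in Appendix Table 3 as conditional on baseline. The footnote then agrees with 6.2.

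The cost is a wording change; the baseline symptom data are already held. There is a small downside: a conditional odds ratio differs from the marginal one and must be read as such, and the sparsest symptoms need the penalised method.

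### The work-productivity model adjusts only for a baseline score in which 0 may also mean out of work; adding baseline work status may gain a little precision

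*SAP*

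**What the plan says.** SAP 6.2 places productivity under "Ordinary least squares (linear) regression" and defines it as "Self-reported work productivity by 0-10 scale on the work questionnaire (people out of work scored to 0"). The same section says that "for continuous and ordinal outcomes these will be adjusted for baseline level of the same outcome". The footnote to Appendix Table 3 repeats the rule ("Adjusted for baseline level of outcome") and names no other covariate. The analysis set is fixed by "the main analysis will be intention-to-treat complete case analysis at 3-month follow-up".

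Baseline work status is listed in Appendix Table 1, so it is collected. It does not enter the productivity model. The SAP does not say separately how the baseline score is coded for people out of work, and it does not say which end of the 0-10 scale is favourable.

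If model assumptions fail badly, "that outcome will be binarized by the median value and analysed with binary logistic regression". Productivity is not one of the two key secondary outcomes, so the additional analyses in section 8 do not cover it.

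**The concern.** A worker who scores 0 and a person without a job have different prospects at 3 months. The worker tends to move back towards the average of people in work, while the person without a job mostly stays at 0. If both carry a baseline value of 0, the model gives them the same prediction. The fitted slope then partly reflects the gap between the out-of-work cluster and people in work, and no longer only how baseline productivity predicts later productivity among workers.

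At stake is residual variance that an already collected covariate could remove, for one secondary outcome in a small trial ("the trial should be halted with the initial 105 patients recruited").

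**Working it through.** **Inputs.** From the SAP: linear regression, own-baseline adjustment, 105 recruited, and 1:1 allocation ("blinded web-based randomisation in 1:1 ratio after initial consent"). The SAP states no SD, correlation, share out of work or power for productivity, so there is no figure to reproduce and everything else is assumed:
- out of work at baseline: 10-50%;
- workers' mean/SD: 3/2.5, 5/2.5 or 7/2, rounded and held within 0-10;
- workers' correlation ρ between baseline and 3 months: 0.3-0.9;
- work status stable (5% leave, 5% return) or with more movement (10% leave, 15% return).

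**When one line is enough.** Let workers at baseline follow a + bX, and let people out of work at baseline have mean c at 3 months. One line through X fits both groups only if a = c. With worker mean m, share staying in work s and share returning r, and ignoring rounding and limits, a ≈ s·m·(1 − ρ) and c = r·m. So a = c when s(1 − ρ) = r:
- stable: 0.95(1 − ρ) = 0.05, so ρ ≈ 0.95;
- more movement: 0.90(1 − ρ) = 0.15, so ρ ≈ 0.83.

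Near those values the indicator adds nothing. Well below them it helps.

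**Misfit in the stable central case** (30% out of work, 5/2.5, ρ = 0.5). The common line is 0.90 + 0.71X; among workers it is 2.41 + 0.47X. At X = 2 the common line predicts 0.90 + 0.71 × 2 = 2.32, and the workers' line 2.41 + 0.47 × 2 = 3.35. For people out of work, c = 0.05 × 5 = 0.25. With stable work status the slopes converge as ρ rises: 0.79 against 0.65 at ρ = 0.7, and 0.87 against 0.84 at ρ = 0.9.

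**Precision.** The relative fall in standard error is 1 − √VR, where VR is the residual variance with the indicator divided by that without it.

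| Scenario | Fall in SE |
|---|---|
| Central case, stable | 4.7% |
| Central case, more movement | 1.9% |
| Most favourable (50% out of work, 5/2.5, ρ = 0.3, stable; VR 0.837) | 1 − √0.837 = 8.5% |
| ρ = 0.7, all scenarios | 0.2-2.1% |
| ρ = 0.9, all scenarios | 0.2% or less |

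A repeat of the grid for this write-up agreed within about 0.2 percentage points.

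**At trial size.** In 4,000 simulated trials of N = 105 (stable central case), the SD of the null estimate fell from 0.421 to 0.402, which is 1 − 0.402/0.421 = 4.5%. Power for a 1-point effect among those working at 3 months rose from 31% to 35%. In another case (30% out of work, 3/2.5, ρ = 0.7, more movement) the SD was 0.346 with either model.

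**Validity.** Under the null, the mean estimate was about 0 and rejection was 4.3-5.9% with either model.

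**Cost if the indicator is useless.** Residual degrees of freedom fall from 102 to 101 at N = 105, a variance factor of about 102/101 = 1.01. Separate simulation at N = 105 gave variance ratios of 1.00-1.02 where scores were very stable, or where ρ was 0.7 or more with high job turnover.

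**The case against.** The strongest reply is that nothing here is invalid. A working model need not fit well for a randomised comparison to be sound, and many covariate lists could be improved in this way. The SAP applies one consistent rule to all its continuous and ordinal outcomes and confines further covariates to section 8.4. Scoring people out of work as 0 may be a deliberate composite. All of this stands. It limits the point to an optional gain in efficiency, and the proposal leaves the outcome coding untouched.

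The median-split fallback is not an answer, because it does not separate the two meanings of 0. If it were triggered, however, the linear-model figures above would no longer apply.

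Three stronger readings are tempting, and the documents support none of them:
- A reader might infer that precision is certainly lost. That depends on correlation, job turnover and share out of work, none of which the SAP gives, and the range includes zero.
- A reader might turn the best corner into sample size (1/0.837 − 1 ≈ 19% more participants). That is an extreme of an assumed grid. The central case gives 1/0.953² − 1 ≈ 10% with stable work status and 1/0.981² − 1 ≈ 4% with more movement.
- A reader might count chance imbalance in work status between arms as a second harm. The two models' estimates differ by the indicator's coefficient times the imbalance left after adjusting for baseline score. Over repeated randomisations this is the same precision loss, not an addition to it.

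**Conclusion.** The point holds as a minor, conditional improvement. On the natural reading that the 0 rule also applies at baseline, one straight line can misfit people in work. There is no bias and no type I error inflation. Under assumed inputs the standard error falls by 0 to about 8%, with about 2 to 5% in the central case at a correlation of 0.5. The gain is negligible when workers' scores are very stable, or when a correlation of about 0.7 or more goes with frequent job changes. Frequent job changes at a correlation of 0.5 reduce the gain but do not remove it. The outcome is not a key secondary one, in a trial that the SAP already expects to be underpowered for its primary outcome.

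**What to change.** Before unblinding, state in 6.2 that the work-productivity model is adjusted for in work at baseline (yes/no) as well as the baseline productivity score, and say that the 0 rule applies at baseline. Name the exception in the Appendix Table 3 footnote. If the change is made after unblinding, 4.1 would require it to be identified as an unplanned analysis.

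No new data are needed. The cost is one degree of freedom, at worst about 1 to 2% of variance, and one outcome that departs from the common own-baseline-only rule.
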